### **Low Marine Omega-3 Diet**

Subjects will be instructed to follow a diet low in marine omega-3s including EPA and DHA. This diet will restrict the following items: fish (salmon, anchovies, swordfish, halibut, tuna, trout, sardines, cod, pollock, catfish, mahi mahi, etc.), shellfish (mussels, oysters, crab, scallops, shrimp, clams, lobster, etc.) and EPA and/or DHA enriched foods, or supplements containing fish or algae oils. If the participant does accidentally consume a restricted food, they will be asked to record the date, time, and amount of food item.

### **Risks and Benefits**

A medical doctor, [name], will be notified immediately of any adverse events and the study coordinator will report any serious adverse events to the OSU IRB and the OSU clinical scientific review committee.

The risk of consuming omega-3 fatty acids in the form of algae oil are extremely low. Omega-3 supplements usually produce only mild side effects such as unpleasant taste, bad breath, bad-smelling sweat, headache, and gastrointestinal symptoms such as heartburn, nausea, and diarrhea. Up to 5 g of EPA and DHA supplements has been concluded to be safe by the Food and Drug Administration. This study utilizes a dose well under 5 g and additional sources of EPA and DHA should be minimized in the diet due to the restrictions of the study.

Omega-3 dietary supplements can interact with certain medications including blood thinners and anticoagulants such as Warfarin. During the screening process, those taking these medications will be screened out and not allowed to participate in the study, minimizing this risk.

We will assess each patient for any adverse event using the Common Terminology Criteria for Adverse Events (version 4.0) from the National Cancer Institute and National Institutes of Health. Patients who develop a grade two adverse event will be asked to stop the intervention. Although unexpected with a food product, if we see 2 similar grade three adverse events, we will stop the study and ask all men and women to discontinue the intervention.

The likelihood of serious adverse events is very low. The compounds in the foods provided are commonly found in a general, varied diet. However, any life-threatening reactions, which may be due to the beverage or supplement and all fatal events while on study or within 30 days of treatment, and the first occurrence of any previously unknown toxicity of any grade will be reported as serious adverse events. The Study Coordinator or data manager will report these reactions within 24 hours to the National Cancer Institute Investigational Drug Branch and the IRB within 10 working days. The principal investigator and the attending physician in collaboration with the NCI, if necessary, will decide if a toxicity is most likely drug related.

The benefits to the participant's health over a short period of time are unknown and likely to be small. In order to compensate participants for time and effort as well as parking and travel costs, we will provide \$20 in cash for the first three clinic visits and \$40 in cash for the final clinic visit and ~~\$16 in cash, \$4 per visits, as reimbursement for one hour of parking in the Wexner Medical Center Garage or Davis Outpatient Garage. parking passes as needed.~~

### **Subject confidentiality**

Strict patient confidentiality of records will be maintained. Random 2-digit numbers will be assigned to each subject and will be used to identify all of that subject's samples and files. Individuals will not be identified by name or by any other personal identifying information in laboratory records, reports, or publications resulting from this study. Thus, risk of disclosure of confidential medical information will be essentially nonexistent. The project team has procedures in place to maintain confidentiality, such as password protected computer access, locked file cabinets and rooms where records are stored, and all team members have received appropriate training, in full compliance with HIPAA. Only the Investigators and study coordinators will have access to any subject data.

Personal data will be kept at least until publication of results, but in most cases is kept longer in case potential follow up studies with the same subject will be designed. Typically, personal information will be shredded after 10 years, and all computer files carrying personal identifying data will be erased.

### **Limitations and Potential Pitfalls**

The capsules will utilize the same oil product (Life's Omega 60 oil, DSM) but will not contain the exact same lot. To standardize the oil as much as possible, the EPA and DHA content of the pills and beverage will be measured, with the oil concentration of the beverage being adjusted to match that of the pill if possible.

### **Internal and External Validity**

Subjects will be stratified by gender and randomized to the study arms to enhance study internal validity. Age, BMI, and initial EPA and DHA levels will be measured in all participants to ensure even distribution across study arms. If differences in these variables are found, they will be used as covariates in data modeling.

Efforts will be made to ensure a diverse sample of study participants by recruiting from various areas around campus and not just recruiting students. Women will represent 50% of the study participants. No participant will be excluded on the basis of race or ethnicity.

### **Data Analysis**

All data analysis will be performed using SAS statistical software.

The impact of the algae oil form on the primary outcome of change in erythrocyte EPA and DHA concentration will be evaluated using analysis of variance (ANOVA). Covariates including BMI, height, weight, sex, age, ethnicity, and pre-trial and baseline levels of EPA and DHA will be evaluated using a forward selection procedure.

The influence of product type on secondary outcomes including EPA and DHA concentrations in other blood lipid pools will also be evaluated using ANOVA.

Compliance will be measured using the daily intake log and number of empty bottles, pills received at each clinic visit. The number of days that the beverage is consumed and any noncompliance with the marine omega-3 restricted diet divided by the number of total days will be used to report compliance.

Exploratory analyses including influence of algae oil vehicle on various blood lipids, hormones, and metabolites and the influence of diet on various variables may also be performed.

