## I. Objectives

The goal of this study is to assess if docosahexaenoic acid (DHA) and eicosapentaenoic acid (EPA) accumulate in blood lipids to the same extent when consumed as a fortified beverage as opposed to a traditional capsule as well as assess compliance to daily consumption, tolerance and acceptability of a fortified soymilk beverage.

It is hypothesized that DHA and EPA levels will be equivalent in erythrocytes after 4 weeks of fortified soymilk consumption as compared to commercial capsules.

We propose the following objectives:

- A. Evaluate the effect of EPA and DHA matrix (beverage or capsule) on accumulation of EPA and DHA in lipid pools over 4 weeks of daily consumption.
  1. EPA and DHA levels will be measured in erythrocytes, peripheral blood mononuclear cells (PBMC), platelets, and plasma over time.
- B. Assess suitability of soymilk as a delivery vehicle for EPA and DHA.
  1. Compliance will be measured using daily intake logs and the return of empty and full bottles of soymilk or remaining capsules
  2. Tolerability will be monitored using a daily symptom journal.
  3. Sensory acceptability will be monitored initially and after 4 weeks of consumption to validate long term use of the fortified soymilk.

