acids. Up to 0.4% algae oil can be added to soymilk with limited changes to overall liking. Consumers did not prefer the control samples over 0.4% algae oil samples at statistically significant levels, meaning that they did not reject those samples. These samples were unflavored and addition of flavoring such as chocolate or vanilla is expected to increase sensory acceptability even more and mask algae oil flavor.

0.4% algae oil in 12 oz. of soymilk equates to approximately 700 mg of combined EPA and DHA (453 mg DHA and 249 mg EPA). In the 2020-2025 Dietary Guidelines for Americans, it was recommended to consume 8-12 oz of seafood per week, providing an average of 250-375 mg of the polyunsaturated fatty acids eicosapentaenoic acid (EPA) and docosahexaenoic acid (DHA). The dietary guidelines cite the reduction in risk of cardiac deaths and beneficial effects for women who are pregnant or breastfeeding as the primary reasons for the seafood recommendation. Based on these recommendations, 700 mg of EPA and DHA should be more than enough per serving. However, many studies looking at the health benefits of EPA and DHA from fish or algae use servings of around 1 gram or higher. Therefore, multiple servings could be given depending on the goals of the clinical trial.

This study will compare the algae oil fortified soymilk to a commercial algae oil capsule containing the same base oil with the goal of demonstrating equivalent or greater accumulation of EPA and DHA in blood lipid pools.

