### *Sample size justification*

- The sample size (10 per group) was calculated based on a one way ANOVA with a meaningful mean difference of 20%, power of 0.80, alpha of 0.05, and a standard deviation of 15% based on literature values of erythrocyte DHA levels . The expected dropout rate is 20%. Therefore, 24 participants will be recruited.

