### **C. Measurement and Instrumentation**

#### **1. Biological Measures**

The EPA and DHA concentration in multiple blood fractions will be measured including erythrocytes, peripheral blood mononuclear cells (PBMC), platelets, and plasma.

Erythrocyte fatty acids concentration correlates better with intake and reflect longer term intake as compared to plasma . Therefore, the primary objective is to determine if erythrocyte DHA and EPA levels differ after consuming algae oil fortified soymilk versus commercial algae oil capsules daily for four weeks.

A total of 24 mL of blood will be collected at each time point into two Vacutainer EDTA tubes (6 mL each) and 2 CPT tubes (8 mL each).

Blood collected into EDTA tubes will be inverted immediately following collection and then stored on ice until centrifugation (within 1 hour of collection). EDTA tubes will be centrifuged at 1932 x g for 10 minutes at 4°C. The plasma will be extracted and aliquoted into 2 mL tubes. Tubes will be stored on ice after aliquoting. The buffy coat layer will be removed and discarded, and the red blood cells will be extracted. The plasma and RBC aliquots will be stored at -80°C until analysis.

Blood collected in the CPT tubes will be prepared according to the manufacturer's instructions. The tubes will be stored upright and centrifuged within 2 hours of collection. The tubes will be inverted before centrifuging at 1800 x g for 30 minutes at room temperature. A portion of the plasma will be removed from the top of the tube and the cells will be resuspended in PBS buffer to a volume of 15 mL. The tube will be inverted to mix and centrifuged again at 300 x g for 15 minutes. The cells will be washed again with PBS. The remaining pellet will be mixed with 1 mL of PBS and then transferred to 2 mL tubes. After centrifuging again at 300 x g for 5 minutes the supernatant will be aspirated off and the cell pellet will be stored at -80°C until analysis.

Fasting blood samples at each time point will be collected into two Vacutainer tube containing EDTA and immediately stored on ice until centrifugation at 1932 x g for 10 min at 4C. Blood will also be collected in one CPT tube to be used for PBMC samples.

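### The protocol hypothesises equivalence of soymilk and capsules, but its primary objective, sample size and primary test address only a difference, with no margin, so the planned test cannot confirm the hypothesis

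*Protocol*

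**What the plan says.** Five places in the protocol bear on this, and they do not agree.

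- **I. Objectives**, the hypothesis: "DHA and EPA levels will be equivalent in erythrocytes after 4 weeks of fortified soymilk consumption as compared to commercial capsules".
- **II. Background and Rationale**: soymilk is compared with capsules "with the goal of demonstrating equivalent or greater accumulation of EPA and DHA in blood lipid pools".
- **III.C.1 Biological Measures**: "the primary objective is to determine if erythrocyte DHA and EPA levels differ after consuming algae oil fortified soymilk", compared with capsules.
- **III.B Sample size justification**: 10 per group, "calculated based on a one way ANOVA with a meaningful mean difference of 20%, power of 0.80, alpha of 0.05". For the variability, this section takes from published work "a standard deviation of 15% based on literature values of erythrocyte DHA levels".
- **Data Analysis**: the "primary outcome of change in erythrocyte EPA and DHA concentration will be evaluated using analysis of variance (ANOVA".

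Two further statements govern covariates. Data Analysis lists body-size and demographic variables, and says that these and "pre-trial and baseline levels of EPA and DHA will be evaluated using a forward selection procedure". Internal and External Validity says of age, BMI and initial EPA and DHA: "If differences in these variables are found, they will be used as covariates in data modeling".

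The protocol states no equivalence or non-inferiority margin, no pair of one-sided tests, and no rule comparing a confidence interval with a limit.

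**The concern.** The first two statements claim similarity, or similarity in one direction. The other three set up a test of whether the arms differ. An ANOVA can reject equality; it cannot establish that a difference is small enough to ignore. A significant result favouring soymilk would support superiority, and so also that soymilk is no worse. A non-significant result shows nothing about equivalence.

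The stated hypothesis therefore has no test. The protocol does not say that non-significance will be read as equivalence, but it offers no other route to that conclusion. Equivalence, non-inferiority and difference can give different verdicts on the same data, so the claim and the margin have to be fixed before the data are seen.

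The scale is also unsettled. The 20% is an effect to detect, and its SD comes from DHA levels, whereas the primary outcome is change, for EPA as well as DHA.

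**Working it through.** **Inputs.** From Sample size justification: n = 10 per group, difference 20%, SD 15%, alpha 0.05, power 0.80. With two groups, the one-way ANOVA F test is the two-sided t test on 18 degrees of freedom.

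**1. The plan's own figure.** SE = 15 × √(2/10) = 6.71. Noncentrality = 20/6.71 = 2.98. Power is 0.805, and solving for n gives 9.89, so 10 per group. The stated size reproduces as a test for a difference.

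**2. What non-significance would mean.** Probability of a non-significant result at 10 per group:

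| True difference | P(non-significant) |
|---|---|
| 5% | 0.89 |
| 10% | 0.71 |
| 15% | 0.44 |
| 20% | 0.195 |

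The last row is the type II error, 1 − 0.805. If non-significance were taken as equivalence, soymilk at the plan's own meaningful difference would pass about one time in five.

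**3. Power under an explicit rule.** The margin is an assumption, since the protocol gives none. Equivalence requires the 90% CI (two one-sided 5% tests) to lie inside ± the margin. Its half-width is about 1.734 × 6.71 = 11.6 points. Non-inferiority requires the lower limit to lie above minus the margin at one-sided 2.5%. True difference 0, SD 15%, one analyte, unadjusted:

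| Margin | Equivalence power at n = 10 | n per group for 0.80 | Non-inferiority power at n = 10 | n per group for 0.80 |
|---|---|---|---|---|
| 20% | 0.78 | 11 | 0.805 | 10 |
| 15% | 0.39 | 18 | 0.56 | 17 |
| 10% | 0.03 | 40 | 0.29 | 37 |

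**4. Whether a CI from the planned model would serve.** Data Analysis lists eight candidate covariates if each analyte is taken with its own levels: BMI, height, weight, sex, age, ethnicity, pre-trial level and baseline level. Simulation: 20 completers, treatment forced in, eight independent noise candidates, true difference −20%, margin 20%, 50,000 runs. The entry levels are assumed, as the protocol gives none.

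| Model for the 90% CI | False equivalence |
|---|---|
| Unadjusted | 5% |
| Pre-specified baseline and sex | 5.1% |
| Forward selection, entry p 0.05 | 7.0% |
| Forward selection, entry p 0.15 | 8.8% |

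Forward selection raises the error above the nominal 5%.

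**5. Power with pre-specified baseline and sex** (20% margin, true difference 0). Equivalence power is 0.74, 0.79 or 0.88 if baseline correlates 0, 0.3 or 0.5 with the outcome (assumed). If both analytes had to pass, which the protocol does not state, power would be 0.61–0.68 unadjusted and 0.54–0.62, 0.62–0.69 or 0.77–0.81 adjusted, for a correlation between analytes from 0 to 0.8.

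**6. The scale of the margin.** Suppose the capsule raises the level by a fraction r of baseline and soymilk delivers nothing. The difference, as a share of the capsule arm's final level, is r/(1 + r). At r = 0.25 this is 0.25/1.25 = 0.20. For any smaller rise, a wholly inactive beverage would truly lie inside a 20% margin on the level scale.

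**The case against.** The best reply is that little needs to change. The plan names a meaningful difference of 20%, which is the quantity a margin would use. At that margin, 10 per group gives non-inferiority power 0.805, the same as the planned test, and equivalence power 0.78. A confidence interval can be read from the ANOVA, and the form of the rule could sit in an analysis plan not shown here. The 19.5% is the type II error the plan already accepts, under a reading it never states. The covariate inflation depends on a CI rule the protocol does not contain and on independent candidates; BMI is in fact computed from height and weight. With assumed correlated candidates it is about 7.0% and 7.9%.

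Much of this stands. The size is nearly adequate at 20%, the 19.5% is conditional, and the covariate point is secondary. It matters mainly because the obvious repair, adding a CI to the planned model, would not hold its error rate.

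The central point remains. The hypothesis, the goal, the primary objective, the sample-size basis and the primary test are all fixed in the protocol, and they conflict. An analysis plan that follows the last three cannot test the hypothesis; one that tests the hypothesis must supply a margin the protocol never set.

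**Conclusion.** The concern holds and must be fixed. The plan as written cannot confirm its own hypothesis, whatever the data show. That conclusion needs no assumption beyond the text.

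The figures do rest on assumptions. All powers take the 15% SD to apply to EPA and to the outcome analysed. The equivalence and non-inferiority figures also assume a margin, and the selection results assume entry levels. With a 20% margin the trial is close to adequate per analyte. It becomes clearly too small if a justified margin is tighter, and power falls if both analytes must pass.

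**What to change.** 1. State one primary claim in Objectives, Background and Biological Measures: equivalence, or non-inferiority if the aim is that soymilk be no worse. If the objective of testing for a difference is kept instead, remove the equivalence hypothesis and goal and say that non-significance will not be read as equivalence. Points 2–5 then do not apply.
2. Pre-specify a margin on a stated scale, level or change, and justify it. The 20% is a candidate; on the level scale it must be weighed against the rise expected with capsules.
3. Base the decision on the CI for soymilk minus capsule: the 90% CI inside both limits, or the lower limit above the negative margin at a stated one-sided alpha. Take it from a model with pre-specified covariates, such as baseline level and the stratification factor sex. The forward-selected model and the rule of adjusting for observed imbalances can remain as sensitivity analyses.
4. Say whether EPA and DHA must both pass.
5. Restate the power in Sample size justification on that rule.

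**Cost.** Wording in five sections, plus a fixed covariate list in place of the data-driven rules in Data Analysis and in Internal and External Validity. Data collection is unchanged. No added enrolment is needed if power is reported as it is: for equivalence within 20% at 10 per arm, 0.78 per analyte unadjusted, or 0.74–0.88 with baseline and sex. Holding 0.80 unadjusted would take 11 completers per arm, whereas 24 recruited with 20% dropout leaves 24 × 0.8 = 19.2 in total. A tighter margin would cost more, as tabulated above. If the difference objective is kept, the cost is wording only.

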### *Body mass index*

Body mass index will be calculated using the weight in kg divided by the square of height in meters.

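### Forward selection among ten covariates in about 20 people makes the primary p-value and confidence interval wrong: type I error is about 8–13%, not 5%, if product type stays in the model

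*Protocol*

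**What the plan says.** Data Analysis states that the "primary outcome of change in erythrocyte EPA and DHA concentration will be evaluated using analysis of variance (ANOVA"). It then lists covariates, namely BMI, height, weight, sex, age, ethnicity, and says that these and "pre-trial and baseline levels of EPA and DHA will be evaluated using a forward selection procedure". No entry level is given, and the text does not say whether product type is held in the model during the search.

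The surrounding text bears on this in four places:

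- Biological Measures: "the primary objective is to determine if erythrocyte DHA and EPA levels differ after consuming algae oil fortified soymilk" rather than capsules.
- Sample size justification: "The sample size (10 per group) was calculated based on a one way ANOVA with a meaningful mean difference of 20" per cent, with "power of 0.80, alpha of 0.05, and a standard deviation of 15" per cent. This is an unadjusted calculation.
- Internal and External Validity: "Subjects will be stratified by gender and randomized to the study arms to enhance study internal validity". For age, BMI and initial EPA and DHA it adds a separate rule: "If differences in these variables are found, they will be used as covariates in data modeling".
- Body mass index: "Body mass index will be calculated using the weight in kg divided by the square of height in meters", so one candidate is computed from two others.

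**The concern.** Forward selection enters, at each step, the covariate that most reduces the residual variance in the data at hand. The final ANOVA then charges one degree of freedom per chosen covariate, as if the set had been named in advance. With ten candidates and about 20 people, the best of ten chance associations can be sizeable. The residual variance comes out too small, the standard error of the product effect is too small, and the test rejects too often.

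The primary objective asks whether the products differ, at alpha 0.05. The risk is therefore a false finding of a difference, and an interval that is too narrow for anyone judging similarity from it. The extra false positives run against the protocol's hypothesis of equivalence, not toward it.

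Three further features are visible in the text. BMI, height and weight all compete although they are linked by definition. Sex, the stratification factor, has no assured place in the model. The imbalance rule can produce a different model from forward selection for the same outcome, and the protocol does not say which governs.

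**Working it through.** **The plan's own figure.** Difference 20, SD 15, two-sided alpha 0.05 (sidedness is not stated; two-sided assumed). With n per group, the noncentrality is 20 / (15·√(2/n)). For n = 10 this is 20 / 6.708 = 2.98 on 18 df, and the noncentral t gives power 0.805. For n = 9 power is 0.757. So 10 per group reproduces. The 24 recruited is 20 × 1.2; dividing by 0.8 gives 25.

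**Candidates.** BMI, height, weight, sex, age and ethnicity make 6. Pre-trial EPA and DHA and baseline EPA and DHA make 4. The total is 10.

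**Procedure simulated.** Start with intercept and product type. At each step take the covariate with the largest F = (RSS_old − RSS_new) / (RSS_new / df_new), and stop when its p-value exceeds the entry level. Then apply the ordinary t-test and 95% interval for product type in the final model.

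**Inputs from the protocol.** 10 per arm, SD of change 15, true difference 0 (type I error) or 20, test at 5%.

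**Assumptions.**
- Entry p 0.05, 0.15 or 0.50.
- Day-0/day-29 correlation 0.5, 0.8 or 0.9.
- Sex effect 0 or 1 SD, with arms balanced by sex.
- Pre-trial/day-0 correlation 0.85 and EPA/DHA correlation 0.6.
- Ethnicity binary at 30%; weight = BMI × height².

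There were 20,000 runs in each of the 3 × 2 = 6 settings. The Monte Carlo standard error at 10% is √(0.10 × 0.90 / 20,000) = 0.002.

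**Results, product type kept in, 10 per arm** (ranges over the six settings):

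| Rule | Type I error | Coverage of nominal 95% CI | Model SE / true SD of estimate |
|---|---|---|---|
| Entry 0.05 | 0.081–0.094 | 0.906–0.919 | 0.85–0.89 |
| Entry 0.15 | 0.107–0.117 | 0.883–0.893 | 0.79–0.81 |
| Entry 0.50 | 0.120–0.126 | 0.875–0.881 | 0.74–0.76 |
| Fixed ANCOVA (day-0 level, sex) | 0.049–0.054 | 0.946–0.951 | 0.99–1.00 |

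Relative to 5%, 0.081 / 0.05 = 1.6 and 0.126 / 0.05 = 2.5. The mean estimate for a true 20 is 19.9–20.1, so there is no bias.

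**Other stopping rules.** Entry 0.01 gives 0.057–0.080, BIC 0.104–0.113 and AIC 0.118–0.124.

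**No dropout (12 per arm).** At entry 0.05 / 0.15 / 0.50: 0.075–0.085 / 0.090–0.100 / 0.100–0.107.

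**Separately coded check.** With correlated covariates at 20 people and no prognostic covariate, type I error was 8.0% at entry 0.05, 10.4% at 0.15 and 13.0% at 0.50. With independent covariates it was 8.7%, 12.7% and 14.5%.

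**Selection does not buy precision.** The true SD of the product estimate is 6.6–7.2 / 6.8–7.6 / 7.9–8.8 at the three entry levels, against 6.0–6.8 for the fixed ANCOVA.

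**Stratification factor.** With a 1 SD sex effect, sex is picked in only 46–49% / 60–65% / 81–84% of runs.

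**BMI, height and weight.** Two or more of the three are picked in under 1% / 2–3% / 28–31% of runs.

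**Imbalance rule alone.** Entering age, BMI and day-0 EPA and DHA when a t-test between arms has p below 0.05, 0.10 or 0.20 gives type I error 0.023–0.050.

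**The case against.** The strongest objection is that the protocol does not say product type is held in the model during selection. If covariates are chosen first and product type is added afterwards, type I error stays at about 5–6%. This is correct. Still, product type is the effect under test and is not among the listed covariates, so keeping it in is the natural reading. The other reading also does harm: a true difference of 20 shrinks to 17.6–18.6 / 16.7–17.5 / 16.3–16.5 at entry 0.05 / 0.15 / 0.50.

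Second, the entry level is a detail a SAP may set, and a strict one reduces the damage. At 0.01 the error can be as low as 5.7%. That stands, and 8% is not an absolute floor. But no stopping rule tried reaches 5% in all settings, and the protocol itself commits the primary model to selection.

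Third, ten candidates is a count of the listed items. If each model were offered only its own fatty acid's levels, there would be eight. That is a less literal reading, and type I error is still 5.7–10.3%.

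Fourth, the imbalance rule does not inflate error, and the two rules might be read as working together. This is accepted: it is an inconsistency to reconcile, not a source of false positives.

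Finally, the estimate is unbiased and the excess errors run against the hoped-for conclusion. This limits the consequence but does not make the p-value or interval valid.

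**Conclusion.** The point holds; the analysis is wrong as written and should be fixed. With product type kept in the model, ten candidates and 10 per arm, the primary test has a type I error of about 8–13% at entry levels from 0.05 to 0.50, or 1.6 to 2.5 times the planned rate. Nominal 95% intervals miss the true difference about 8–12% of the time. The error falls to about 6–8% at entry 0.01 and to 7.5–10.7% if nobody drops out.

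These figures rest on product type being forced in and on the assumed entry levels and correlations. The direction does not depend on the particular values tried. On the alternative reading the test keeps its level but the estimated difference is pulled toward zero, so neither reading gives a sound primary result.

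**What to change.** For the primary analysis, replace the forward-selection sentence in Data Analysis and the imbalance rule in Internal and External Validity with text such as:

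> Change in erythrocyte EPA and DHA concentration from day 0 to day 29 will be analysed by ANCOVA with product type, the day-0 level of the same fatty acid measure, and sex (the stratification factor) as fixed terms. No covariate selection will be used.

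The day-0 to day-29 contrast follows the four-week intervention and its visit days. The wording leaves open whether EPA and DHA are analysed jointly or separately. Other covariates can go into one labelled sensitivity analysis, with BMI standing in for BMI, height and weight together. Age, BMI and initial levels should be described by arm but not used to choose the model.

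The cost is two sentences of text and two model degrees of freedom; day-0 levels and sex are already collected. Power at 10 per arm is 0.88 / 0.81 / 0.80 for a day-0/day-29 correlation of 0.5 / 0.8 / 0.9. The unadjusted analysis has 0.80–0.81 with no sex effect, or 0.72–0.73 with a 1 SD sex effect. The precision gain may therefore be nil when the correlation is high, but the error rate returns to 5%. The change should be made before outcome data are seen.
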